### **8.3.9 Relevant Medical History and current Medical Conditions / Signs and Symptoms**

The number and percentage of patients with relevant medical history/current medical conditions will be presented by system organ class (SOC) and preferred term (PT) in the SAF.

Signs and Symptoms with CTCAE grade will be also presented by system organ class (SOC) and preferred term (PT) in the SAF.

Tables will be presented by SOC sorted in alphabetic order and PTs within SOC sorted by descending number of counts according to the overall column.

## **8.4 Stratification factors**

No stratification is planned in this study

## **8.5 Protocol deviation**

### **8.5.1 Protocol deviation eligibility criteria**

Deviations from Protocol eligibility criteria collected in the eCRF will be summarized and listed by treatment arm.

### **8.5.2 Protocol deviation summaries**

The number and percentage of patients in the SAF with important protocol deviations will be tabulated by the deviation type and category. All protocol deviations will be listed.

Any protocol deviations impacting statistical analyses will be classified as major. All these protocol deviations for included patients will be presented by patient in data listings with a distinction between deviations at inclusion and deviations during the study. The number of patients with at least one major protocol deviation will be summarized by type and overall, with a distinction between deviations at inclusion and deviations during the study (Section 6.2).

## **8.6 Treatments**

The treatment information will be based on the SAF population.

### **8.6.1 Study treatment**

Duration of TG4050 exposure, number of TG4050 injections and Relative Dose Intensity (RDI) will be provided by listing. The total number of injections will also be displayed.

The safety population will be used for all listings of study treatment.

## **8.6.2 Prior and Concomitant medications**

### **8.6.2.1 Prohibited and/or restricted medications during study treatment**

The following medications are prohibited (unless utilized to treat a drug-related adverse event):

- Immunosuppressive agents
- Immunosuppressive doses of systemic corticosteroids (except refer protocol)
- Any concurrent anti-neoplastic therapy (i.e. chemotherapy, hormonal therapy, immunotherapy, radiation therapy, or another standard or investigational agents for treatment of ovarian cancer)
- Any live vaccine for the prevention of infectious disease
- Any other investigational agent

The following non-drug therapies must not be used during the study (and within 28 days before the start of trial treatment):

- Herbal remedies with immunostimulating properties (e.g., mistletoe extract) or known to potentially interfere with major organ function (e.g., hypericin)
- Major surgery

These medications and non-drug therapies will be tracked in the listings of concomitant medications and medical history to identify potential deviations.

### **8.6.2.2 Prior and/or Concomitant medications**

Prior and concomitant medications are:

- Medications and/or non-drug therapies taken by the patient prior to start TG4050, continuing or not after the start of the study treatment
- All medications and non-drug therapies taken during the treatment period of the study starting from Day 1 up to 30 days after the last study treatment administration

Prior and concomitant medications will be coded using the WHO Drug Dictionary using latest available including the Anatomical Therapeutic Chemical (ATC) classification and will be listed and summarized by active ingredient by means of frequency counts and percentages.

A table with the frequency and percentage of patients with medications started before D1 ongoing or not at D1 and a second table with the frequency and percentage of patients with Concomitant medications started on or after D1 will be displayed.

The SAF will be used for all above mentioned concomitant medication tables.

## **8.6.3 End of treatment (EOT) and End of study (EOS) visits**

### **8.6.3.1 End of treatment**

The following information will be listed for each patient and will be summarized with:

SAP-template version of 4 Jan 2024

- Primary reason for study treatment discontinuation (Maximum number of TG4050 administered / Documented progressive disease / Adverse Event / Investigator's decision / Protocol deviation / Patient's consent withdrawal / Lost to follow-up / Other)
- Date of start/end of treatment (in listing only)

#### **8.6.3.2 End of study**

The following information will be listed for each patient:

- Primary reason for study completion/discontinuation
- Date of study completion (listing only)
- Date of death (listing only)
- Primary cause of death (Underlying disease / Not Known / Other)

### **8.7 Analysis of patients not treated**

In case of TG4050 individualized product unavailability in due time or TG4050 manufactured product not administered for any reason, the reason will be documented as a Failure to provide or a Failure to treat and the patient will be withdrawn from the study. The patient will continue to benefit from routine medical monitoring and will receive SOC in case of recurrence as per normal practice.

- **Failure to treat**

Patients who cannot receive TG4050 at the time of planned treatment will be listed. The reason that prevents a patient from being treated will be recorded. Reasons can be Inclusion/exclusion criteria for treatment period not met, lost to follow-up, ICF withdrawn, Adverse Event or Failure to provide. The reason of failure to treat will be listed by type (SCOS report and eCRF page “End of study”).

- **Failure to provide**

Patients for whom TG4050 cannot be provided according to the SCOS report will be listed. Reasons for not being able to provide the vaccine will also be recorded. Reasons for failure to provide can be any issue at any step of TG4050 production. The reason of failure to provide will be listed by type (SCOS report and eCRF page “End of study”).

### **8.8 Analysis of efficacy**

- **Time to measurable relapse will be analyzed according to RECIST 1.1**

The time from the date of C1D1 to the date of first detection of recurrence documented by imaging procedures, whichever occurs first (a sensitive analysis could be performed on the time to measurable relapse including the death due to ovarian cancer). Time to measurable disease will be censored if no recurrence is observed at the cut-off date for analysis. For patients who stopped the study treatment before documentation of disease progression, tumor assessment should be performed every 9 weeks until

documented disease progression according to RECIST 1.1.

[figure not shown]
The censoring date will be the date of the last evaluable tumor assessment before the cut-off date.

- **Tumor response according to RECIST 1.1. (in case at least one non measurable lesion is present at baseline)**

Tumor response will be evaluated according to RECIST 1.1. Tumor assessment will be performed within 21 days prior to treatment start and then every 9 weeks until documented disease progression and will require CT-scans of the pelvis and abdomen and (X-ray or preferably CT-scan) of the chest. MRI can be used for patients who are allergic to radiographic contrast media. Throughout the study, the same assessment technique must be used. Response will be displayed, and results will be listed

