## 2.2. Secondary objectives

To evaluate:

- Failure to provide TG4050
- Failure to treat with TG4050
- CA-125 doubling time and half-life as appropriate, time to normalization and response according to GCIG criteria
- Time to measurable relapse in Cohort A and Time to progression in Cohort B per RECIST 1.1
- Tumor response by using RECIST 1.1

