#### 2.1.2 Treatment period

A treatment period with TG4050 monotherapy will start in:

- Cohort A: when patients develop an asymptomatic relapse defined on the basis of progressive serial elevations of serum CA-125 (GCIG criteria) or documentation of low volume radiological disease with CA-125 > ULN. Low volume radiological disease is defined as radiologically visible disease excluding intra-hepatic or intra-splenic metastases, ascites or pleural effusion thought to require drainage.
- Cohort B: when patients develop an asymptomatic relapse with measurable disease excluding intra-hepatic or intra-splenic metastases, ascites or pleural effusion thought to require drainage, whatever serum CA-125 level and for whom further treatment is not planned within 2 months. Longest

diameter on CT-scan must not exceed 2 cm for non-nodal lesions and 2.5 cm in short axis for nodal lesions.

Patients will receive TG4050 up to a total of 20 injections or until documented disease progression as defined by RECIST 1.1 justifying treatment with chemotherapy, or unacceptable toxicity including occurrence of a dose-limiting toxicity, or patient withdrawal for any reason, whichever occurs first.

All treated patients will be followed for:

- Safety assessments performed on a weekly basis for the first 6 weeks and every 3 weeks thereafter.
- Serum CA-125 levels assessed in an accredited central laboratory within 7 days prior to treatment initiation and every 3 weeks after start of study treatment.
- Imaging performed within 21 days prior to treatment initiation, at day 43 and every 9 weeks after study treatment start.
- Immune responses evaluated in the blood at baseline and on days 8, 22, 43, 64, 85 and 211; in the tumor at the time of documented disease progression according to RECIST 1.1.

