### 3.2 Secondary objectives

Secondary endpoints are to evaluate the rate of failure to provide TG4050 and failure to treat with TG4050, to evaluate, if applicable, the CA-125 doubling time/time to normalization (this analysis won't be performed given the low number of evaluable patients ) and response according to GCIG criteria and time SAP-template version of 4 Jan 2024

to measurable relapse in cohort A and time to progression in cohort B per RECIST 1.1 and the tumor response according to RECIST 1.1.

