  - Every 9 weeks with a time widow of +/- 7 days from start of treatment, CT-scan or MRI of the abdomen and pelvis are mandatory. Brain and chest CT are to be performed if lesions are suspected.

Progressive disease: as documented on tumor assessment according to RECIST 1.1.

Progressive disease will be determined according to RECIST (version 1.1) based on local evaluations. Lesions (non-target) identified at baseline, if any, will be followed post-baseline. The appearance of new lesions will also be investigated if clinically indicated.

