**Tumor response:**

Tumor response status assessments will be evaluated by imaging performed every 9 weeks from first TG4050 administration until documented progression. Only tumor assessments performed before the start of further antineoplastic therapies (i.e. any additional secondary antineoplastic therapy or surgery) will be considered.

Per RECIST 1.1, the method used at baseline should match at all subsequent assessments, but, for a number of reasons such as site error (e.g. switch from MRI to CT) or renal dysfunction (making contrast a risk), this will not always be done. A strict implementation of RECIST would mean that any change in imaging method compared to one used at baseline should lead to unknown overall response at given assessment.

The number and percentage of patients with complete response among patients with non-measurable lesion at baseline will be presented.

**End of study:** The end of study is defined as the date of the last patient last visit (including safety follow-up visit). The end of study form in the eCRF will be filled in when patient withdraws the study due to any reason.

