## **8 STATISTICAL METHODS**

### **8.1 General principles**

Statistical summaries will be produced using SAS® software version 9.4. The tables, listings and graphics will be prepared in landscape format.

Drafts TFLs will be produced and reviewed before the database lock to ensure that no data is missing and to check for potential inconsistency in the database.

Continuous variables will be described using the number of observations (N), arithmetic mean (Mean), standard deviation (sd), minimum (MIN), median (Median), the interquartile range (Q1-Q3) and maximum (MAX). Means will be further described with 95% confidence intervals (CIs) where appropriate. One additional decimal point for mean, median, Q1 and Q3, and 2 additional decimal points for sd will be used. Data with more than 3 decimal places (if any), may not follow this rule: so, 3 decimal places will be used.

Categorical variables will be summarized by frequency (N) and percentage (%). Proportions will be estimated with their exact (Clopper-Pearson) 95% CIs when appropriate.

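### SAP Appendix 1 codes measurable disease as a major deviation and SAP 8.8 ties RECIST response to a non-measurable lesion, although measurable disease defines Cohort B; the relapse event is also worded two ways

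*SAP*

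**What the plan says.** **Objectives.** Protocol 2.2 lists "Tumor response by using RECIST 1.1" as a secondary objective, and Protocol 9.3.2 repeats it as an endpoint; neither restricts it by lesion type. SAP 3.2 names "time to progression in cohort B per RECIST 1.1 and the tumor response according to RECIST 1.1".

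**Cohorts.** SAP 2.1.2 has "Cohort B: when patients develop an asymptomatic relapse with measurable disease", subject to size limits and organ exclusions. Protocol 4.1 agrees. Cohort A is entered on CA-125 alone, or on low-volume visible disease with CA-125 above the upper limit of normal (ULN).

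**Response.** The SAP 8.8 heading reads "Tumor response according to RECIST 1.1. (in case at least one non measurable lesion is present at baseline", and the paragraph ends "Response will be displayed, and results will be listed". SAP 7.6.1 adds "The number and percentage of patients with complete response among patients with non-measurable lesion at baseline will be presented" and, under progressive disease, "Lesions (non-target) identified at baseline, if any, will be followed post-baseline".

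**Deviations.** Appendix 1 code EXCL07 is RECIST 1.1 measurable disease, criticality Major, with no exception by cohort. INC10, also Major, describes only the Cohort A relapse routes. SAP 6.2 removes a patient with a major deviation from the Evaluable Per-Protocol Set (EPP). Protocol exclusion 7 bars measurable disease only where symptoms have appeared that justify starting further treatment.

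**Event.** SAP 7.6.2 ends the relapse clock at relapse or documented progression, whichever is earlier. SAP 8.8 ends it when recurrence is first seen on imaging.

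**The concern.** Cohort B patients are the ones certain to have measurable lesions, and so the ones in whom shrinkage or stability of target lesions can be judged. The SAP's response text leaves them out unless they also carry a non-measurable lesion, and the only response count it states is complete response in patients with non-measurable disease. No reason is given.

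The same gap appears in the deviation list. A code that makes Cohort B's entry condition a major deviation could put protocol-eligible patients into the study report as major deviators and produce a wrong EPP count.

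The event wording matters mainly for patients whose disease is already visible on the baseline scan: all of Cohort B, and Cohort A patients entering with low-volume disease. Neither SAP section says how that disease counts, and Cohort B's time to progression has no derivation of its own. With six treated patients, each response and each event date is a large share of the efficacy information.

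**Working it through.** There is no sample size, power or error rate to reproduce; SAP 7.1 states that none is planned. The check compares texts, with simple counts for size.

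**1. EXCL07 against the protocol**
- Protocol exclusion 7: measurable disease *and* symptoms justifying further treatment.
- Protocol 4.1 and SAP 2.1.2, Cohort B: measurable disease *without* symptoms is the entry route.
- EXCL07: measurable disease, with no mention of symptoms. Every Cohort B patient meets it by definition.

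**2. INC10 against the protocol**
- It flags anyone who meets neither Cohort A route. A Cohort B patient with CA-125 above ULN has visible disease and so satisfies the second route. One with CA-125 at or below ULN satisfies neither and is flagged, although Protocol 4.1 admits Cohort B at any CA-125 level.

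**3. How many patients**
- Treated patients: 6 (SAP 4). The split by cohort is not given, so let k be the number in Cohort B, an assumption ranging from 0 to 6.
- Share flagged by EXCL07 through Cohort B = k/6. Most that can remain in the EPP on this criterion = 6 − k.

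| k | flagged | EPP at most |
|---|---|---|
| 0 | 0% | 6 |
| 1 | 16.7% | 5 |
| 2 | 33.3% | 4 |
| 3 | 50.0% | 3 |
| 4 | 66.7% | 2 |
| 5 | 83.3% | 1 |
| 6 | 100% | 0 |

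- The Cohort A low-volume route does not exclude measurable lesions, so a Cohort A patient could be caught as well; the documents give no number.

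**4. Response**
- The condition is at least one non-measurable lesion, so a Cohort B patient with both lesion types qualifies. Only measurable-only patients fall outside.
- For them, SAP 10.2 still provides Listings 16.2.6.3 to 16.2.6.5 on the safety set (SAF), without a lesion-type limit. SAP 10.1 lists no RECIST response table for anyone; its efficacy displays are two CA-125 figures.

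**5. Event date, hypothetical patient with disease visible at baseline**
- Formula (SAP 7.6.2): (event date − first injection date + 1)/30.4375, which is study day/30.4375.
- If visible disease is counted as recurrence at the Day 43 scan: 43/30.4375 = 1.41 months.
- If the event is progression at the next scan on the protocol schedule, Day 43 + 63 = Day 106: 106/30.4375 = 3.48 months. Nominal gap: 63/30.4375 = 2.07 months.
- With Day 43 ± 1 and Day 106 ± 7, the gap is 99 − 44 = 55 to 113 − 42 = 71 days, or 1.81 to 2.33 months. With ± 7 on both it is 99 − 50 = 49 to 113 − 36 = 77 days, or 1.61 to 2.53 months.
- SAP 2.1.2 counts the nine weeks from treatment start, which puts the scan after Day 43 at Day 64: 64/30.4375 = 2.10 months, a gap of 21/30.4375 = 0.69 months.

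**The case against.** Four stronger readings are tempting, and the documents do not carry them.

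*Every Cohort B patient will be misreported and the efficacy analysis emptied.* SAP 8.5.1 reports deviations from the protocol's eligibility criteria as collected in the eCRF, and under those an asymptomatic Cohort B patient is no deviator. Appendix 1 calls its list anticipated and SAP 6.2 calls it non-exhaustive, and text in 6.2 next to the EPP exclusion rule is redacted. Protocol 9.4.2 names the EPP for efficacy, but no efficacy or safety output listed in the SAP uses it. Misreporting is possible, not certain, and would show in Tables 14.1.1.4 and 14.1.1.2.

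*Response data in measurable disease are lost.* They are not: the SAF listings hold each patient's assessments. What is missing is a stated summary. SAP 3.2 also places *if applicable* before its run of endpoints, and it is unclear whether those words reach tumor response; Protocol 2.2 and 9.3.2 have no such qualifier.

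*The complete-response percentage is seriously imprecise.* SAP 8.1 says "Proportions will be estimated with their exact (Clopper-Pearson) 95% CIs when appropriate", but no table or figure for that percentage is listed, so an interval would describe a display that is not planned.

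*The event wording shifts relapse by about two months.* The size depends on the visit windows and on which scan schedule applies. The shorter time also needs a strained reading, since a lesion already on the baseline scan is not first detected at Day 43. For Cohort B, SAP 3.2 and the RECIST definition of progression in 7.6.1 already point to progression. The ambiguity is mostly in Cohort A patients with visible disease.

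What remains is text that contradicts the protocol or itself and is cheap to correct.

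**Conclusion.** The point holds as a reconciliation issue of minor impact. EXCL07 and INC10 do not match Protocol 4.1 and 4.2 for Cohort B. The response text in SAP 8.8 and 7.6.1 is limited to non-measurable disease without a stated reason. The relapse event has two wordings and no rule for disease visible at baseline.

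The consequences are confined to descriptive secondary endpoints and deviation reporting in 6 patients. The primary safety analysis, on the SAF, is unaffected. The size rests on the assumed k: with k = 0 no Cohort B patient is misreported, and only a Cohort A patient with measurable low-volume disease or visible baseline disease could still be touched; with k = 6 a literal EXCL07 flags all six. The number of measurable-only patients is also not given. The month figures illustrate one hypothetical patient and are not an estimate of bias.

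**What to change.** SAP only.

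1. Reconcile EXCL07 and INC10 with Protocol 4.1 and 4.2 so that both cohorts are covered. No new eligibility rule is proposed.
2. In 8.8, delete the parenthetical condition on non-measurable lesions. In 7.6.1, extend the complete-response sentence and the non-target lesion sentence to all baseline lesions. List best RECIST 1.1 response for every SAF patient with a baseline lesion, with a category for unknown or not evaluable, because 7.6.1 itself foresees unknown response after a change of imaging method.
3. Use one event wording in 7.6.2 and 8.8, judged against the baseline scan: RECIST 1.1 progression for Cohort B, and the existing 7.6.2 event for Cohort A, with a statement that disease already visible at baseline is not itself an event. Show baseline RECIST status beside the date in Listing 16.2.6.5. This keeps to events the SAP already names; the study has stopped, so a new endpoint rule should not be introduced now.

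The cost is SAP wording, two corrected codes and added listing columns, all from scans already collected.

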## **8.9 Exploratory endpoints and analyses: translational research**

**CCI**

A large rectangular area of the page is completely blacked out, indicating redacted content. To the left of this redacted area, the acronym 'CCI' is printed in a bold, black, sans-serif font.

## **8.10 Safety analyses for the treatment period**

The primary objective is to evaluate the safety and tolerability of multiple subcutaneous (SC) injections of a neoantigen-directed active immunotherapy (TG4050) in ovarian, fallopian or peritoneal high-grade serous carcinoma (HGSC) patients with asymptomatic relapse.

All safety analyses will be performed and summarized in the SAF.

### **8.10.1 Adverse Events (AEs)**

#### **8.10.1.1 Definitions**

##### **Adverse Event (AE):**

An Adverse Event is defined as any new untoward medical occurrence or worsening of a preexisting medical condition in a clinical investigation patient administered study treatment and that does not necessarily have a causal relationship with this treatment. An AE can therefore be any unfavorable and unintended sign (such as an abnormal laboratory finding), symptom, or disease temporally associated with the use of study treatment, whether or not considered related to the study treatment.

##### **Treatment-emergent adverse Event (AE):**

A treatment-emergent adverse event (TEAE) is defined as a sign or symptom that emerges during treatment or within 30 days of the last dose of the study drug, having been absent pre-treatment or that has worsened relative to the pre-treatment state. Any adverse event deemed related to study drug will also be considered a TEAE regardless of elapsed time since last study drug dose.

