##### 8.2.2.1. **Definitions**

###### Treatment-Emergent Adverse Event (TEAE)

A treatment-emergent adverse event (TEAE) is defined as a sign or symptom that emerges during treatment or within 30 days after the last dose of the study drug, having been absent pre-treatment or that has worsened relative to the pre-treatment state.

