###### Adverse events

AE summaries will include all TEAEs corresponding to AEs that have started on or after the day of first study treatment administration or that have worsened on or after first TG4050 administration and starting no later than 30 days after the date of last study treatment administration. All AEs, significant AEs, AEs leading to discontinuation of study treatment, severe AEs (Grade 3 or 4) and serious AEs (SAE) will be listed and summarized by System Organ Class (SOC) and Preferred Term (PT), intensity (based on the NCI CTCAE grades, relationship to TG4050).

Written narratives will be produced for all SAEs and unexpected or other significant AEs that are judged to be of special interest because of their clinical importance.

Adverse events/SAEs occurring after signing the Informed Consent Form (ICF) but before starting study treatment, including those observed in patients screened but not included will be listed separately from those occurring after treatment start.

SAEs occurring more than 30 days after administration of the last dose of TG4050 and evaluated by the investigator as related to TG4050 will be listed separately.

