### 8.10.1.2 AEs analysis

#### Adverse Events

AE summaries will include all TEAEs corresponding to AEs that have started on or after the day of first study treatment administration or that have worsened on or after first TG4050 administration and starting no later than 30 days after the date of last study treatment administration.

For these analyses, the number and percentage of patients with at least one AE will be summarized in a frequency table by System Organ Class (SOC) and Preferred Term (PT) as per MedDRA dictionary. The number of events will also be summarized in the same table. Tables will be presented by SOC sorted in alphabetic order and PTs within SOC sorted by descending number of counts according to the overall column.

Written narratives will be produced for all SAEs and unexpected or other significant AEs that are judged to be of special interest because of their clinical importance.

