#### Serious Adverse Events (SAEs)

SAEs occurring after signing the Informed Consent Form (ICF) but before starting study treatment, including those observed in patients screened but not included will be listed separately from those occurring after treatment start.

AEs or SAEs occurring more than 30 days after administration of the last dose of TG4050 and evaluated by the investigator as related to TG4050 will be flagged.

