##### a. Listings

All AEs will be listed with the following items:

- Patient Number
- Age
- Verbatim, Preferred term (PT) and System Organ class (SOC)
- Date of onset and date of end (study day)
- Duration of the AE in days
- Outcome (Recovered / Recovered with sequelae / Not recovered / Fatal / Unknown / Worsening)
- Evaluation of seriousness (Yes/No)
- Date of seriousness
- Intensity grade (Grade 1/ Grade 2 / Grade 3 / Grade 4 / Grade 5)
- Injection Site Reaction (Yes / No)
- Related to other study procedure (Yes /No)
- Dose Limiting Toxicity (Yes / No)

- Relation to TG4050 (Related/ Not Related)
- Action taken regarding TG4050 (None / Delayed / cancelled / Stopped / Not applicable)
- Action regarding the event (none, hospitalization....)

Moreover, the following sub-listings will be provided:

- Dose Limiting Toxicity AEs
- TG4050-related AEs
- SAEs
- TG4050-related SAEs
- AEs leading to discontinuation
- Grade 3/4 adverse events
- Fatal AEs
- Deaths
- Pre-treatment SAEs

b. Tables

An overview table will be provided with the number and percentage of patients for each of the following categories (the number of events will be also provided):

- with at least one AE
- with dose limiting Toxicity AEs
- with at least one AE related to TG4050
- with at least one injection site reaction
- with at least one AE related to other study procedure
- with at least one AE leading to treatment discontinuation
- with at least one AE related to TG4050 and leading to treatment discontinuation
- with at least one SAE
- with at least one SAE related to TG4050
- with at least one grade 3/4 AE
- with at least one grade 3/4 AE related to TG4050
- with fatal AE

---

 Related : reasonable possibility

 Not related : no reasonable possibility

The number and percentage of patients for each category listed above will be summarized in a frequency table by body system organ class (SOC) and preferred terms (PT) as per MedDRA dictionary. The number of events will be also summarized in the same table.

Table for AEs, AEs related to TG4050 will also be presented by grade and summarized in a frequency table by body system organ class (SOC) and preferred terms (PT) as per MedDRA dictionary.

Tables will be presented by SOC sorted in alphabetic order and PTs within SOC sorted by descending number of contents according to the overall column.

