## 10 LIST OF TABLES, FIGURES AND LISTINGS

### 10.1 Tables, figures and graphs

Table number	Title
14.1	DEMOGRAPHIC DATA
14.1.1	patients disposition
Table 14.1.1.1	Screen failure and non-inclusion reason – SCR
Table 14.1.1.2	Study populations
Table 14.1.1.3	Summary of protocol deviations – SCR
Table 14.1.1.4	Summary of protocol deviations – SAF
14.1.2	Demographic and Baseline characteristics
Table 14.1.2.1.1	Demographic data and study entry characteristics – SCR
Table 14.1.2.1.2	Demographic data and baseline characteristics – SAF
Table 14.1.2.2	Relevant Medical History and current Medical Conditions – SAF
Table 14.1.2.3	Signs and symptoms at baseline – SAF
Table 14.1.2.4.1:2	Prior anti-cancer therapies – SCR/SAF
Table 14.1.2.5	Vital signs and clinical examination – SAF
14.2	EFFICACY DATA
14.2.1	CA-125 Evolution
Figure 14.2.1 – 1	Waterfall plot for best percentage change of CA-125 – SAF
Figure 14.2.1 – 2	Evolution of CA-125 between Screening period and Treatment period – SAF
14.3	SAFETY DATA
14.3.1	Displays of adverse events
Table 14.3.1.1	Summary of adverse events – SAF
Table 14.3.1.2	Number (%) of patients with adverse events by cohort - SAF
Table 14.3.1.3	Number (%) of patients with adverse events by grade – SAF
Table 14.3.1.4	Number (%) of patients with adverse events related to TG4050 by grade – SAF
Table 14.3.1.5	Number (%) of patients with injection site reactions by grade – SAF
Figure 14.3.1.6	Adverse events by patient – SAF
14.3.2	Listings of deaths, other serious and significant adverse events
Table 14.3.2.1	Adverse events leading to treatment discontinuation, listing – SAF
Table 14.3.2.2	Adverse events due to DLT, listing – SAF
Table 14.3.2.3	Serious adverse events, listing – SAF
Table 14.3.2.4	Serious adverse events related to TG4050, listing – SAF
Table 14.3.2.5	Grade 3/4 adverse events, listing – SAF
Table 14.3.2.6	Fatal Adverse Events, listing – SAF
Table 14.3.2.7	Deaths, listing – SAF
14.3.3	Narrative of deaths, other serious and certain other significant adverse events
14.3.4	Abnormal Laboratory Value (each patient)
Table 14.3.4.1	Laboratory parameters Grade 3-4, listing – SAF

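### The SAP has two rules for late related adverse events, and its pre-treatment SAE listing leaves out undosed patients

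*SAP*

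**What the plan says.** **Late related events.** The protocol (8.2.2.1) defines a TEAE as one that "emerges during treatment or within 30 days after the last dose of the study drug", or a pre-existing condition that worsens; it makes no exception for related events. The SAP (8.10.1.1) keeps that window and adds: "Any adverse event deemed related to study drug will also be considered a TEAE regardless of elapsed time since last study drug dose". For the summaries, SAP 8.10.1.2 takes all TEAEs and then limits them to events "starting no later than 30 days after the date of last study treatment administration". Protocol 9.4.1 sets the same limit. For SAEs beyond 30 days, protocol 9.4.1 says those "evaluated by the investigator as related to TG4050 will be listed separately"; SAP 8.10.1.2 says of AEs or SAEs beyond 30 days that those "evaluated by the investigator as related to TG4050 will be flagged".

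**Pre-treatment SAEs.** SAP 8.10.1.2 and protocol 9.4.1 both want SAEs between consent and first dose listed separately, and both extend this to screened patients who never entered treatment. SAP 10.2 assigns Listing 16.2.7.3 (SAEs before treatment) to the SAF. SAP 6.1 restricts the SAF to patients with at least one dose.

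**Pre-treatment deaths.** Protocol 9.4.1 (Fatal Events) asks for a separate listing of fatal events before treatment in patients not included. The SAP has no matching text or named output.

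**The concern.** Adverse events graded by CTCAE are the primary endpoint (protocol 9.3.1), so the rule for which events count should be single and unambiguous. Here the definition and the summary rule use the same term and give different answers for the same event. A programmer has to choose, and the choice decides whether a late related SAE appears in the overview row "with at least one SAE related to TG4050". Table 14.3.2.4, "Serious adverse events related to TG4050, listing", would show that event either way, because it is a listing and no time limit is set for it.

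On the second point, a listing built to its stated population cannot show the undosed patients whom the SAP's own text names. On the third, an output the protocol calls for is not named in the SAP.

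**Working it through.** The plan gives no figure to reproduce; SAP 7.1 has no sample size calculation. The check sets the texts side by side and adds a small illustration.

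**1. A related SAE starting on day 31 or later after the last dose**

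| Text | Result |
|---|---|
| Protocol 8.2.2.1 | Not a TEAE |
| Protocol 9.4.1 | Not summarised; listed separately |
| SAP 8.10.1.1 | A TEAE |
| SAP 8.10.1.2, summaries | Not summarised |
| SAP 8.10.1.2, listings | Listed and flagged |

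The third and fourth rows conflict, because the summaries are said to cover all TEAEs.

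**2. Can such an event reach the database?** Yes. Protocol 8.2.2.2 collects related SAEs beyond 30 days and ends their entry in the eCRF only at database lock. For other related AEs the same section collects up to the safety follow-up visit. Under protocol 6.2.6 that visit falls at the latest on day 30 + 14 = 44, so at most 44 − 30 = 14 days lie beyond the limit. Footnote 7 of Appendix II B stops AE reporting at 30 days, so even those 14 days are uncertain. That conflict over collection is a separate matter for the protocol to reconcile.

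**3. Size, as an illustration.** SAP section 4 gives 6 treated patients. Suppose one of them had her only related SAE after day 30.

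- 30-day rule: 0/6 = 0%. Exact 95% upper limit = 1 − 0.025^(1/6) = 45.9%.
- Open-ended definition: 1/6 = 16.7%. Exact 95% lower limit = 1 − 0.975^(1/6) = 0.4%; upper limit = 97.5th percentile of Beta(2, 5) = 64.1%.

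The row moves by 16.7 percentage points. No such event is reported in the documents.

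**4. Population of Listing 16.2.7.3.** Required: consented patients, dosed or not. Labelled: SAF, so dosed patients only. The label is not shorthand for everyone, since the same list uses SCR or SCR/SAF where undosed patients are meant (Listings 16.2.1.1, 16.2.4.1.1:2 and 16.2.6.2).

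**5. Pre-treatment deaths in undosed patients.**

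- A fatal event recorded as an SAE belongs in Listing 16.2.7.3 once that listing is on the SCR.
- A death known only from the End of study page has no dedicated place. SAP 8.6.3.2 lists date and cause of death, but section 8.6 works on the SAF and Listing 16.2.5.4 is labelled SAF.
- What remains is an entry as a reason in Listing 16.2.1.1 or 16.2.6.2, both on the SCR.

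**The case against.** The best defence on late events is that SAP 8.10.1.2 is the specific rule for summaries and so governs the tables, with the flag explaining any difference from the listings. That gives a workable reading, and it keeps the consequence small. It does not remove the contradiction, because the summary rule relies on the term that 8.10.1.1 defines more widely. A broader safety definition is also a legitimate choice, provided that it is applied throughout and declared as a departure from the protocol.

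On deaths, the defence is largely right. SAP 8.7 offers its reasons as possibilities, not as a closed list, and draws on the End of study page, which protocol 4.4 says is completed when a patient dies. Before first dose, protocol 8.2.2.2 collects only serious reactions to a protocol-required procedure, namely the screening blood sample, so a pre-treatment listing would be short on any population.

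Four stronger readings are tempting and not supported:

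- **Late related events are lost.** They are not; they remain in the listings, flagged.
- **The DLT counts change with the TEAE rule.** Beyond the run-in the DLT definition does use the term treatment-emergent. But SAP 8.10.1.2 carries DLT as a Yes/No item for each event, and nothing says it is derived from TEAE status.
- **All AE summary tables are materially exposed.** Table 14.3.1.5, "Number (%) of patients with injection site reactions by grade", is formally under the same rule, but a reaction first appearing more than 30 days after the last injection is remote.
- **The undosed patients left out can be counted by subtracting 6 from the planned 60 or so.** The number screened is not given, and the study stopped for low inclusion.

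**Conclusion.** Two defects stand on the text. The SAP's TEAE definition and its summary window contradict each other for related events starting after day 30, and Listing 16.2.7.3 has a population that cannot meet the SAP's own requirement. The missing output for pre-treatment fatal events in undosed patients is a minor addition, mostly cured by correcting that population.

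The practical effect is small and the change is optional in rank (COULD). The first defect has an effect only if a related event, most likely an SAE, starts after day 30 and is entered before lock. The second and third matter only if an undosed patient had a pre-treatment SAE or died. The documents report neither. The shift of 16.7 percentage points assumes one affected patient among the 6 treated and illustrates sensitivity; it is not an observed result.

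**What to change.** Before lock:

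1. Use one TEAE rule in SAP 8.10.1.1 and 8.10.1.2. Either delete the final sentence of the TEAE definition and list late related events separately, as protocol 9.4.1 does for SAEs, or extend the summary rule to include them and declare the departure from the protocol.
2. Change the population of Listing 16.2.7.3 from SAF to SCR and flag fatal events in it.
3. Show date and cause of death for undosed patients, from the End of study page, in an SCR listing. Tables 14.3.2.6 and 14.3.2.7 can stay on the SAF.

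Separately, reconcile protocol 8.2.2.2 with Appendix II B footnote 7 on AEs between day 31 and the safety follow-up visit.

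The cost is a sentence or two of SAP wording, one population label and one short listing, which may turn out empty. No new data are needed. The one drawback is that keeping the open-ended definition obliges the SAP to state that it departs from the protocol.
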